3.2 Study Activities (Years 2 and 3 Treatment Visits)

		Yes	ar 2			Yes	ar 3				
Visit	9	10	11	12	13	14	15	16			
Study Week (±7 days)	60	72	84	96	108	120	132	144			
Tests and Assessments ¹											
Physical Examination	X	X	X	X	X	X	X	X			
Vital Signs	X	X	X	X	X	X	X	X			
Hematology	X	X	X	X	X	X	X	X			
Blood Chemistry	X	X	X	X	X	X	X	X			
Urine Pregnancy Test ²	X	X	X	X	X	X	X	X			
Urinalysis	X^3	X ³	X ³	X^3	X ³	X^3	X^3	X^3			
Brain MRI ⁴ □ Gd ⁵		Scl	neduled MRI sca	ns were perfor	med in protocol	versions 1 throug	gh 6.				
EDSS	X	X	X	X	X	X	X	X			
Visual Function Test	X	X	X	X	X	X	X	X			
SF-36 and EQ-5D				X				X			
Dispense Study Treatment (BG0012)	X	X	X	X	X	X	X	X			
Concomitant Therapy and Procedures Recording		Monitor and record throughout the study as per Protocol Section 11.6									
AE/SAE Reporting			Monitor and	record through	out the study as	per Protocol Sec	ction 15				

AE = adverse event; EDSS = Expanded Disability Status Scale; EQ-5D = EuroQol EQ-5D Health Survey; Gd = gadolinium; MRI = magnetic resonance imaging; SAE = serious adverse event; SF-36 = Short-form 36 Health Survey.

- 1. Tests and assessments must be completed prior to BG00012 distribution.
- 2. For women of childbearing potential. Results must be known prior to BG00012 distribution.
- 3. If urinalysis is abnormal, see Protocol Section 11.2.
- 4. Only in subjects who had MRI scans as part of Studies 109MS301 and 109MS302 and in 109MS303 up through and including Amendment 6.
- 5. MRI must not be performed within 30 days of receiving a course of steroids.

3.3 Study Activities (Years 4 Through 8 Treatment Visits)

Year		Ye	ar 4			Ye	ar 5			Yea	ar 6			Yea	ar 7			Yea	ar 8	
Visit	17	18	19	20	21	22	23	24	25	26	27	28	29	30	31	32	33	34	35	36 ¹
Study Week (±7 days)	156	168	180	192	204	216	228	240	252	264	276	288	300	312	324	336	348	360	372	384
Tests and Assessments ²																				
Physical Examination		X		X		X		X		X		X		X		X		X		X
Vital Signs	X	X	X	X	X	X	X	X	X	X	X	X	X	X	X	X	X	X	X	X
Hematology					Sec	e Section	n 3.5													
Blood Chemistry		X		X		X		X		X		X		X		X		X		X

Urine Pregnancy Test ³		X		X		X		X		X		X		X		X		X		X
Urinalysis		X^4		X^4		X^4		X^4		X^4		X^4		X^4		X^4		X^4		X^4
Brain MRI^5 Scan \pm Gd^6						Scheo	duled M	RI scar	is were	perform	ed in p	rotocol	versions	s 1 thro	ugh 6.					
EDSS		X		X		X		X		X		X		X		X		X		X
Visual Function Test		X		X		X		X		X		X		X		X		X		X
SF-36 and EQ-5D				X				X				X				X				X
Dispense Study Treatment (BG00012) ⁷	X	X	X	X	X	X	X	X	X	X	X	X	X	X	X	X	X	X	X	
	1																			

Concomitant Therapy and Procedures Recording

Monitor and record throughout the study as per Protocol Section 11.6

AE/SAE Reporting Monitor and record throughout the study as per Protocol Section 15

AE = adverse event; CRF = case report form; EDSS = Expanded Disability Status Scale; EQ-5D = EuroQol EQ-5D Health Survey; Gd = gadolinium; MRI =

to monitor lymphocytes on study.

- 2. Tests and assessments must be completed prior to BG00012 distribution.
- 3. For women of childbearing potential. Results must be known prior to BG00012 distribution.
- 4. If urinalysis is abnormal, see Protocol Section 11.2.

magnetic resonance imaging; SAE = serious adverse event; SF-36 = Short-form 36 Health Survey.

1. For subjects who have already completed Visit 36 (or beyond), an End of Study Visit should be completed 4 weeks after their next visit (scheduled or unscheduled), regardless of further need

- 5. Only in subjects who had MRI scans as part of Studies 109MS301 and 109MS302 and in 109MS303 up through and including Amendment 6.
- 6. MRI must not be performed within 30 days of receiving a course of steroids.
 7. The date and Study Visit/Week at which subjects are switched to open-label treatment should be recorded on the dosing CRF.

3.4 Study Activities for Subjects Who Already Completed Visit 36

For subjects who have already completed Visit 36 (or beyond) prior to Protocol Version 8, an End of Study Visit should be completed 4 weeks after their next visit (scheduled or unscheduled), regardless of further need to monitor lymphocytes on study. For subjects who have not completed Visit 36 prior to Protocol Version 8, Visit 36 will serve as the last scheduled Visit and an End of Study Visit should be completed 4 weeks after their next visit (scheduled or unscheduled), regardless of further need to monitor lymphocytes on study.

Year		Yes	ar 9			Yea	r 10			Year	· 11		Year 12			
Visit	37	38	39	40	41	42	43	44	45	46	47	48	49	50	51	52
Study Week □7 days)	396	408	420	432	444	456	468	480	492	504	516	528	540	552	564	576
Tests and Assessments ¹																
Physical Examination		X		X		X		X		X		X		X		X
Vital Signs	X	X	X	X	X	X	X	X	X	X	X	X	X	X	X	X
Hematology						See Protoc	col Section	ı 4.5								
Blood Chemistry		X		X		X		X		X		X		X		X
Urine Pregnancy Test ²		X		X		X		X		X		X		X		X
Urinalysis		X^3		X^3		X^3		X^3		X^3		X^3		X^3		X^3
Brain MRI ⁴ Scan ± Gd ⁵				•	Schee	duled MR	I scans we	re perfor	ned in pro	tocol versi	ons 1 thre	ough 6.				
EDSS		X		X		X		X		X		X		X		X
Visual Function Test		X		X		X		X		X		X		X		X
SF-36 and EQ-5D				X				X				X				X
Dispense Study Treatment (BG00012) ⁷⁶																
Concomitant Therapy and Procedures Recording	Monitor and record throughout the study as per Protocol Section 11.6															
AE/SAE Reporting		Monitor and record throughout the study as per Protocol Section 15														

AE = adverse event; CRF = case report form;

; EDSS = Expanded Disability Status Scale; EQ-5D = EuroQol EQ-5D Health Survey; Gd =

gadolinium; MRI = magnetic resonance imaging; SAE = serious adverse event; SF-36 = Short-form 36 Health Survey.

- 1. Tests and assessments must be completed prior to BG00012 distribution.
- 2. For women of childbearing potential. Results must be known prior to BG00012 distribution.
- 3. If urinalysis is abnormal, see Protocol Section 11.2.
- 4. Only in subjects who had MRI scans as part of Studies 109MS301 and 109MS302 and in 109MS303 up through and including Amendment 6.
- 5. MRI must not be performed within 30 days of receiving a course of steroids.
- 6. The date and Study Visit/Week at which subjects are switched to open-label treatment should be recorded on the dosing CRF.

3.5 Study Activities (Hematology and Analysis: Year 4 Through End of Treatment Visits)

Tests and Assessments	Subjects With Lymphocyte Count ≥LLN	Subjects With Lymphocyte Count <lln mm3</lln>	Subjects With Lymphocyte Count <500/mm ³
Hematology	Every 12 weeks	Every 12 weeks	Every 4 or 12 weeks per Protocol Table 3
Bone Marrow Biopsy (optional)	Not applicable	Not applicable	Optional procedure ⁶
LLN = lower l	mit of normal;		

6. See Protocol Section 11.3 for further details

3.6 Study Activities 109MS303 (Unscheduled and Post-Treatment Visits)

Tests and Assessments	End of Study Visit ¹	Unscheduled Relapse Assessment Visit ²	Premature Study Treatment Withdrawal Visit ³	Lymphocyte Follow-Up (Up to 96 Weeks After Last Dose) ⁴
Physical Examination		X	X	
Vital Signs	X	X	X	X
Hematology	X^3	X	X^3	X
Blood Chemistry	X	X	X	
Urine Pregnancy Test ⁵	X	X	X	
Urinalysis	X^6	X^6	X^6	
Brain MRI ⁷ Scan ± Gd ⁸	Schedu	aled MRI scans were performed i	in protocol versions 1 through	6.
EDSS		X	X	
Visual Function Test		X	X	
SF-36 and EQ-5D		X	X	
Relapse Assessment		X		
Concomitant Therapy and Procedures Recording	N	Monitor and record throughout th	e study as per Protocol Section	n 11.6
AE/SAE Reporting		Monitor and record throughout the	he study as per Protocol Section	on 15

AE = adverse event; EDSS = Expanded Disability Status Scale; EQ-5D = EuroQol EQ-5D Health Survey; Gd = gadolinium; LLN = lower limit of normal; MRI = magnetic resonance imaging; SAE = serious adverse event; SF-36 = Short-form 36 Health

Survey

- 1. For subjects who have already completed Visit 36 or beyond, an End of Study Visit should be completed 4 weeks after their next visit (scheduled or unscheduled).
- 2. Unscheduled Relapse Assessment Visit is to be carried out within 5 days of suspected relapse.
- 3. Subjects who permanently discontinue BG00012 prior to Week 384 (Visit 36) should complete a Premature Study Treatment Withdrawal Visit within 4 weeks of their last dose. The Premature Study Treatment Withdrawal Visit will serve as the End of Study Visit.
- 4. Lymphocyte follow-up as per Protocol Section 11.3.
- 5. For women of childbearing potential.
- 6. If urinalysis is abnormal, see Protocol Section 11.2.
- 7. Only in subjects who had MRI scans as part of Studies 109MS301 and 109MS302 and in 109MS303 up through and including Amendment 6.
- 8. MRI must not be performed within 30 days of receiving a course of steroid.

4 INTERIM ANALYSIS

This statistical analysis plan (SAP) is intended to describe the planned analysis methods and considerations for the final analysis based on data after the database lock. Interim analyses were performed as needed for regulatory reporting, safety updates, publications, or as otherwise required by the Sponsor. One specific interim analysis was conducted to provide an assessment of the long-term safety and efficacy profile of BG00012 at the time of filing the MS application. This interim analysis was based on all data collected for subject visits, assessments, and evaluations through August 3, 2011. After that, several interim analyses were conducted based on data snapshots without formal database lock, and these results were presented for publications purposes to assess long-term safety and efficacy profile of BG00012.

5 SAMPLE SIZE JUSTIFICATION

There is no formal sample size calculation. The number of subjects eligible for this study is determined by the number of subjects who participated in and completed Studies 109MS301 and 109MS302.

Subjects randomized to BG00012 in Study 109MS301 or 109MS302 continued on the same BG000012 dose in this extension study. Subjects randomized to placebo in Study 109MS301 or 109MS302 or glatiramer acetate in Study 109MS302 were randomized to BG00012 in a 1:1 ratio to 240 mg BID or 240 mg TID in this extension study. Randomization was stratified by previous study and previous treatment (i.e., 3 strata: Study 109MS301 placebo, Study 109MS302 placebo, and Study 109MS302 glatiramer acetate).

All patients receiving BG00012 240 mg TID were switched to BID (approved dosage) at their next study visit after regulatory approval (effective March 2013).

6 STATISTICAL ANALYSIS METHODS

Descriptive summary statistics will be used throughout. For continuous endpoints and parameters, summary statistics will generally include: number of subjects with data, mean, standard deviation, median, and range. For categorical endpoints and parameters, summary statistics will generally include: number of subjects with data and the number and percentage of those with data in each category.

Summaries will generally include all available data included in the database lock for this final analysis. However, as this is an ongoing study, caution must be exercised when interpreting analyses at later timepoints for which sample sizes may be relatively sparse. Kaplan-Meier curves will display results through timepoints for which a sufficient number of subjects at risk exists in each treatment group (e.g., at least 20 subjects at risk per treatment group).

The statistical software, SAS®, will be used for all statistical analyses. The SAS code for efficacy analyses is not provided in this statistical analysis plan, as the code is similar to that provided in the statistical analysis plans for Studies 109MS301 and 109MS302.

6.1 Statistical testing procedures

As this final analysis of a long-term extension study, analyses will generally be descriptive in nature and will be based on observed data, without imputation for missing values. For relevant efficacy analyses, confidence intervals will be provided for each treatment group where appropriate to characterize the variability around the point estimate. Statistical hypothesis testing may be completed for selected analyses and will be considered exploratory.

Missing measurements

In general, no imputation for missing measurements will be performed, unless specified otherwise.

Missing dates

For start date of adverse events, if all available start date information is the same as that of the date of first dose in 109MS303, and the event did not end prior to first dose, the date of first dose in 109MS303 will be used as the imputed date. Otherwise for adverse events, and always for the start of concomitant medications, the earliest possible start date based on available partial information will be used. Namely, if only the day is missing, the 1st of the month will be used; if the month is also missing, January 1st will be used. End dates for concomitant medications and adverse events will not be imputed. For evaluations other than adverse events and concomitant medications, missing or incomplete dates that are needed for analysis will also be imputed. If the day is missing for a study procedure or assessment but the month and year are present, the day will be imputed as the 15th of the month. Month and year will not be imputed for study procedures or assessments. These same rules will be applied to missing or incomplete dates for relapses.

6.2 Analysis populations, Treatment groupings, and Datasets

6.2.1 Analysis populations

The analysis populations of Study 109MS303 that will be utilized are described below.

- Study 109MS303 Intent-to-Treat (ITT) Population: This analysis population is defined to include all subjects who entered Study 109MS303 and received at least one dose of study treatment in Study 109MS303. Subjects will be analyzed in the treatment groups to which they were randomized/assigned. This will be the primary analysis population utilized for the majority of baseline analyses and non-MRI analyses addressing long-term efficacy and persistence of efficacy.
- Study 109MS303 MRI Cohort: This analysis population is defined to include subjects in the Study 109MS303 ITT Population who consented to participate in the MRI substudy and have any MRI data in Studies 109MS301, 109MS302, or 109MS303. This will be the primary analysis population utilized for the majority of MRI analyses addressing long-term efficacy and persistence of efficacy.
- Study 109MS303 Safety Population: This analysis population is defined to include all subjects who had any post-baseline safety follow-up in Study 109MS303, defined

as any treatment emergent AE in Study 109MS303 or any post-baseline laboratory, vital signs, or physical exam assessment in Study 109MS303, and received at least one dose of study treatment in Study 109MS303. Subjects will be analyzed in the treatment groups to which they were randomized/assigned.

6.2.2 Treatment Groupings

The analysis populations described above in Section 6.2.1 will be utilized in conjunction with the following three sets of treatment groupings as appropriate:

- Combined Treatment Grouping, indicating the study treatments during Study 109MS301 or 109MS302 and Study 109MS303 combined:
 - BG00012 240 mg BID -> 240 mg BID (i.e., BG00012 240 mg BID in both studies), or, alternatively, BG00012 240 mg BID Previously Treated with BG00012 240 mg BID;
 - BG00012 240 mg TID -> 240 mg TID (i.e., BG00012 240 mg TID in both studies), or, alternatively, BG00012 240 mg TID Previously Treated with BG00012 240 mg TID;
 - Placebo -> BG00012 240 mg BID (i.e., placebo in Studies 109MS301/302 and BG00012 240 mg BID in Study 109MS303), or, alternatively, BG00012 240 mg BID Previously Treated with Placebo;
 - Placebo -> BG00012 240 mg TID (i.e., placebo in Studies 109MS301/302 and BG00012 240 mg TID in Study 109MS303), or, alternatively, BG00012 240 mg TID Previously Treated with Placebo;
 - GA -> BG00012 240 mg BID (i.e., GA in Study 109MS302 and BG00012 240 mg BID in Study 109MS303), or, alternatively, BG00012 240 mg BID Previously Treated with GA;
 - GA -> BG00012 240 mg TID (i.e., GA in Study 109MS302 and BG00012 240 mg TID in Study 109MS303), or, alternatively, BG00012 240 mg TID Previously Treated with GA.

Analyses utilizing the Study 109MS303 ITT Population, Study 109MS303 MRI Cohort, or Study 109MS303 Safety Population may employ Combined Treatment Grouping. The first treatment group name in each bullet above (e.g., BG00012 240 mg BID -> 240 mg BID) will be utilized for relevant efficacy summaries, while the second treatment group name in each bullet above (e.g., BG00012 240 mg BID Previously Treated with BG00012 240 mg BID) may be utilized for relevant safety summaries.

- Study 109MS303 Treatment Grouping, indicating the study treatment during Study 109MS303:
 - o BG00012 240 mg BID;

- o BG00012 240 mg TID; and
- o Total BG00012 (i.e., BG00012 240 mg BID and BG00012 240 mg TID groups combined).

Analyses utilizing the Study 109MS303 Safety Population may employ Study 109MS303 Treatment Grouping. This treatment grouping will be utilized for select safety analyses where the incidence of an event or abnormality in Study 109MS303 itself may be of interest.

Baseline summaries will include both Combined Treatment Grouping and Study 109MS303 Treatment Grouping.

6.2.3 Datasets

The analysis populations and treatment groupings described above in Sections 6.2.1 and 6.2.2, respectively, will be utilized in conjunction with the following three datasets as appropriate:

- Combined Data, defined as data from Studies 109MS301, 109MS302, and 109MS303; and
- Study 109MS303 data only, defined as data from Study 109MS303.

Analyses utilizing Combined Treatment Grouping may include either Combined Data or Study 109MS303 data only. Analyses utilizing Study 109MS303 Treatment Grouping will include Study 109MS303 data only.

6.2.4 Summary of Use of Analysis populations, Treatment groupings, and Datasets

The following table summarizes the use of analysis populations by treatment groupings and datasets, with a brief mention of the planned analyses in italicized text in brackets:

Table 6.2.4.1: Summary of use of analysis populations by treatment groupings and datasets

	Treatmen	t Grouping
Dataset	Combined Treatment Grouping	Study 109MS303 Treatment Grouping
Combined Data	Study 109MS303 ITT Population [Majority of Non-MRI Efficacy Analyses] Study 109MS303 MRI Cohort [Majority of MRI Efficacy Analyses]	N/A
Study 109MS303 data only	Study 109MS303 ITT Population [Study 109MS303 ARR Analysis] Study 109MS303 Safety Population [Majority of Safety Analyses]	Study 109MS303 Safety Population [Selected Safety Analyses]

Notes: Italicized text in brackets provides a brief description of the analyses planned for the particular combination of analysis population, treatment grouping, and dataset.

Lymphocyte analysis may be utilized with Combined Data and Combined Treatment Grouping or Study 109MS303 Treatment Grouping. N/A = Not Applicable.

6.3 Description of Analytic Methods

6.3.1 Analysis of Baseline Data

Baseline data will be summarized utilizing the Study 109MS303 ITT Population and both Combined Treatment Grouping and Study 109MS303 Treatment Grouping. The definition of baseline will be dependent on the analysis performed and the study data utilized.

The following are the various definitions of baseline that may be utilized in analyses:

- Study 109MS303 Baseline is defined as the latest available value prior to or on the date of first dose of study treatment in Study 109MS303;
- Previous Study Baseline is defined as the latest available value prior to or on the date of first dose of study treatment in Study 109MS301 or 109MS302; and
- BG00012 Treatment Baseline is defined as the latest available value prior to or on the date of first exposure to BG00012, specifically:

- the latest available value prior to or on the date of first exposure to study treatment in Study 109MS301 or 109MS302 for subjects on BG00012 treatment in Study 109MS301 or 109MS302;
- o the latest available value prior to dosing in Study 109MS303 for subjects in the placebo or GA treatment groups in Study 109MS301 or 109MS302.

6.3.2 Accounting of Subjects

The following categories of accounting will be summarized for Study 109MS303 using numbers and percentages:

- Subjects who entered the study;
- Subjects who were dosed;
- Subjects who discontinued treatment (and therefore withdrew from study), along with reasons for discontinuing treatment; and
- Subjects who have lymphocyte follow up.

Listings of subjects who discontinued treatment and withdrew from the study and the reasons for discontinuation/withdrawal will be presented.

6.3.3 Protocol Deviations

Protocol deviations identified in the study will be listed.

6.3.4 Demographic and Baseline Characteristics

Demographic characteristics, including age (years), age category (18-19, 20-29, 30-39, 40-49, 50-55, and >55, as well as <40, ≥40), gender, and race, will be summarized. In addition, region, height (cm), weight (kg), and body mass index (kg/m^2) will also be summarized. Weight, height, and body mass index will be presented based on the Study 109MS303 Baseline definition, while age will be presented based on both the Previous Study Baseline (corresponding to the age covariate used in efficacy models) and Study 109MS303 Baseline definitions.

Baseline disease characteristics will also be summarized, including MS disease history (time since first MS symptoms and time since diagnosis of MS at Study 109MS303 Baseline), relapse history (number of relapses in the past 12 months and in the past 3 years at Previous Study Baseline), McDonald criteria (at Previous Study Baseline), and EDSS score (at both the Previous Study Baseline and Study 109MS303 Baseline). In addition, summary statistics for baseline MRI parameters(number and volume of Gd-enhancing lesions, number and volume of T2 lesions, number and volume of T1 lesions, normalized whole brain volume, and median MTR of whole brain) for the Study 109MS303 MRI cohort will also be presented, as applicable, at both the Previous Study Baseline and Study 109MS303 Baseline.

Prior MS treatment history and baseline cardiac risk factors will also be summarized based on the Previous Study Baseline definition.

6.3.5 Medical History

An updated medical history is collected at the baseline visit of Study 109MS303. A summary of this updated medical history will be presented.

6.3.6 Study Drug Compliance and Time on Study

Study drug compliance in Study 109MS303 will be summarized. The number of capsules not taken since the previous visit (out of those capsules the subject was expected to take) is collected on the study drug accountability CRF page. Using this information, percentage compliance will also be calculated as follows:

Total number of capsules not taken is calculated as the sum of all individual values of the number of capsules not taken since the previous visit for a subject, as defined above.

Total number of capsules assigned is calculated based on the number of days on study medication for a subject. The calculation of number of days on study medication is detailed below.

Percentage compliance is then calculated as: [(Total number of capsules assigned) – (Total number of capsules not taken)] / (Total number of capsules assigned) * 100.

Percentage compliance will be calculated up to the date of last dose in Study 109MS303.

In addition, the total time on study medication will be summarized as a continuous variable and categorized into intervals. Days on study medication is calculated as the number of days from date of first dose to date of last dose. Additionally, the total number of subject-years of exposure to study medication will be presented. Time on study medication will be summarized for Study 109MS303 only and for Combined Data, utilizing the Study 109MS303 ITT and Safety populations.

Time on study parameters, including overall time on study and time on study prior to first use of alternative MS medication, will be summarized as a continuous variable and categorized into intervals. Total number of subject-years for time on study, both overall and prior to first use of alternative MS medication, will also be presented with respect to the dataset analyzed. The last known date on study will be taken as the last visit/evaluation date from relevant data for a subject. Summaries will be performed for Study 109MS303 only and for Combined Data, utilizing the Study 109MS303 ITT population. Additionally, overall time on study in Study 109MS303 will be summarized utilizing the Study 109MS303 Safety population.

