**Table 3: Lymphocyte Monitoring and Management for Subjects Who Have a Lymphocyte Count  $<500/\text{mm}^3$**

For subjects who have a lymphocyte count  $<500/\text{mm}^3$ , the Investigator should repeat the test as soon as possible. If re-test confirms that the lymphocyte count remains  $<500/\text{mm}^3$ , lymphocyte counts should be monitored every 4 weeks while on BG00012.

If subject has lymphocyte counts  $<500/\text{mm}^3$  for  $\geq 24$  weeks, subject meets the **Temporary Withholding Rule** and BG00012 will be temporarily withheld. If the Temporary Withholding Rule is not met, the subject will be monitored every 12 weeks.

CONFIDENTIAL

The information contained herein may not be used, disclosed, or published without the written consent of Biogen MA Inc.

Lymphocyte Monitoring for Subjects Meeting the Temporary Withholding Rule	Management for Subjects Meeting the Temporary Withholding Rule

The subject will be monitored every 4 weeks for 24 weeks, then every 12 weeks until the lymphocyte count is <math>\geq</math>LLN OR for 96 weeks after their last dose, whichever is earlier. However, if a subject reaches the end of study and their lymphocyte count remains <math><</math>LLN, the subject will be monitored every 12 weeks until the lymphocyte count is <math>\geq</math>LLN OR for 48 weeks after their last dose, whichever is earlier.
	
 
• If lymphocyte count remains <math><500/\text{mm}^3</math> for 24 weeks after temporary withdrawal, BG00012 must be permanently discontinued.
 
• If lymphocyte count is between <math>\geq 500/\text{mm}^3</math> and <math>\leq 800/\text{mm}^3</math>, then BG00012 will continue to be temporarily withheld.
 
• If lymphocyte count recovers to <math>>800/\text{mm}^3</math> (confirmed by 2 tests, at least 4 weeks apart), the physician/patient has the option to restart BG00012. If, upon resumption of BG00012, the lymphocyte count is <math><500/\text{mm}^3</math> on 1 occasion (confirmed by repeat testing), then BG00012 must be permanently discontinued.
 
• Alternative disease-modifying treatmenta may be considered, at the discretion of the treating physician as per standard of care. Subjects treated with alternative disease-modifying treatment will not have the option to restart BG00012.
 

AE = adverse event; CRF = case report form; LLN = lower limit of normal.

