2 STUDY DESIGN

2.1 Study Overview

The first phase of this extension study is a multicenter, parallel-group, randomized, dose-blind, dose-comparison study. The second phase of the study is an open-label phase during which all subjects receive BG00012 at a dose of 240mg BID. A total of 1738 subjects with relapsing-remitting multiple sclerosis have been randomized at approximately 375 sites in North America, Europe, and the rest of the world.

Eligible subjects from Studies 109MS301 and 109MS302 were enrolled in this extension study and were followed for up to 8 years, assuming BG00012 continues to have a positive benefit/risk ratio.

All subjects received either:

- BG00012 240 mg BID (2 capsules [120 mg each] twice a day and 2 placebo capsules once a day); or
- BG00012 240 mg TID (2 capsules [120 mg each] 3 times a day).

Subjects randomized to BG00012 in Study 109MS301 or 109MS302 continued on the same BG000012 dose in this extension study.

Subjects randomized to placebo in Study 109MS301 or 109MS302 or glatiramer acetate (GA) in Study 109MS302 were randomized to BG00012 in a 1:1 ratio to 240 mg BID or 240 mg TID in this extension study.

With regulatory approval (effective March 2013), all patients receiving BG00012 240 mg TID switched to BID (approved dosage) at their next study visit. This study became an open label extension study with the approved dosage BG00012 240 mg BID.

Subjects who switched to an alternate approved MS therapy in Study 109MS301 or 109MS302 were randomized/enrolled in this extension study as outlined above according to their original treatment group in 109MS301 or 109MS302.

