2.2 Overall Study Duration and Follow-Up

Eligible subjects were enrolled at Week 96 (Visit 24) of their previous BG00012 study (109MS301 or 109MS302), which would serve as the Baseline Visit for this extension study. If the Baseline Visit could not be combined with Visit 24 of their previous BG00012 study, the subjects may have been randomized within 6 months of Visit 24, provided that they still were eligible for enrollment. The Baseline visit assessments may have been repeated if there was a gap in study treatment.

Subjects reported to the study site every 4 weeks for the first 24 weeks (Visit 1 through Visit 6) and every 12 weeks thereafter for up to 8 years.

Subjects who completed the Week 384 visit (Visit 36), regardless of further need to monitor lymphocytes on study, completed an End of Study Visit at Week 388 ± 7 days. For subjects who have completed Visit 36, an End of Study Visit was completed 4 weeks after their next visit (scheduled or unscheduled), regardless of further need to monitor lymphocytes on study. Subjects who permanently discontinued BG00012 prior to Week 384, regardless of further need to monitor lymphocytes on study, completed a Premature Study Treatment Withdrawal Visit within 4 weeks after their last dose of BG00012. Subjects who completed BG00012 treatment or permanently discontinued BG00012 for any reason and who had a lymphocyte count <LLN were not withdrawn from the study. These subjects were followed according to Protocol Section 11.3.

For subjects who have already completed Visit 36 (or beyond) prior to the Protocol Version 8, an End of Study Visit was completed 4 weeks after their next visit (scheduled or unscheduled), regardless of further need to monitor lymphocytes on study. For subjects who have not completed Visit 36 prior to Protocol Version 8, Visit 36 served as the last scheduled Visit and an End of Study Visit was completed 4 weeks after their next visit (scheduled or unscheduled), regardless of further need to monitor lymphocytes on study.

Premature Study Withdrawal Visits and Unscheduled Relapse Assessment Visits were performed as necessary. All efforts were made to keep the subjects' visit schedule relative to their Baseline Visit (Day 1). All subjects who discontinued the study treatment were considered to be prematurely withdrawn from the study.

The end of study is defined as the Last Patient, Last Visit for final collection of data for the primary outcome

2.3 **MRI**

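### Exposure is counted as a first-to-last-dose span, so withheld-then-restarted periods count as dosed time, and Combined Data may also count the entry gap and parent-study time off BG00012

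*SAP*

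**What the plan says.** SAP 6.3.6 gives one rule for exposure: "Days on study medication is calculated as the number of days from date of first dose to date of last dose". Total subject-years of exposure are presented with it. On scope, "Time on study medication will be summarized for Study 109MS303 only and for Combined Data".

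Compliance uses the same day count. "Total number of capsules assigned is calculated based on the number of days on study medication for a subject", whereas "The number of capsules not taken since the previous visit (out of those capsules the subject was expected to take) is collected" on the accountability page. Percentage compliance is assigned minus not taken, divided by assigned, up to the last 109MS303 dose. Its scope is narrower than that of exposure: "Study drug compliance in Study 109MS303 will be summarized".

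The design puts off-drug time inside such a span in three ways.

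- **Withholding then restart.** Protocol 11.2.1 allows up to two laboratory-driven interruptions. Protocol 11.2.3 covers resumption after a 2- to 4-week interruption for flushing or GI events. In Protocol Table 3, for counts from 500 to 800/mm³, "then BG00012 will continue to be temporarily withheld", with no maximum stated there, and restart is an option after confirmed recovery above 800/mm³.
- **Entry gap.** When baseline could not be combined with parent Visit 24, "the subjects may have been randomized within 6 months of Visit 24" (SAP 2.2). Protocol 7.2.1 foresees that BG00012 may be interrupted in this interval.
- **Parent-study switchers.** "Subjects who switched to an alternate approved MS therapy in Study 109MS301 or 109MS302 were randomized/enrolled in this extension study" according to their original treatment group (SAP 2.1).

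**The concern.** The primary objective is the long-term safety profile. Subject-years and duration categories tell the reader how much BG00012 treatment lies behind it. A span from first to last dose can only equal or exceed the time actually dosed, so any error in exposure goes one way. It falls on identifiable subjects: those who restarted after lymphopenia or another interruption and, in Combined Data, those who entered late or had stopped BG00012 in the parent study. Such subjects can land in too long a duration category even when the total hardly moves.

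The compliance formula is also internally inconsistent. Assigned capsules accrue on every day of the span, while missed capsules are counted only among those the subject was due to take. A day on which drug was withheld by rule then enters as fully taken.

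**Working it through.** The documents give no exposure or compliance result, so there is no figure to reproduce. The SAP formulas are applied directly. Off-drug durations, the true compliance of 90% and cohort shares are assumptions. The 384 weeks (SAP 2.2), 96 parent-study weeks (Protocol 5.2) and 1738 subjects (SAP 2.1) come from the documents.

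**Notation.** S = span in weeks, w = off-drug weeks inside it, c = true compliance on days when dosing was due.

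**1. Exposure, 109MS303 only.** Overstatement = S/(S − w) − 1, with S = 384:
- w = 4: 384/380 = +1.1%
- w = 8: 384/376 = +2.1%
- w = 24: 384/360 = +6.7%
- w = 48: 384/336 = +14.3%
- w = 96: 384/288 = +33.3%

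A shorter course magnifies the effect: w = 24 in S = 96 gives 96/72 = +33.3%. A withholding never followed by restart has w = 0, because the last dose precedes it.

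**2. Compliance, 109MS303 only.** Missed capsules are proportional to (1 − c)(S − w), so SAP compliance = c + (1 − c)w/S. With c = 90%, S = 384:
- w = 24: 0.90 + 0.10 × 24/384 = 90.6%
- w = 96: 0.90 + 0.10 × 96/384 = 92.5%

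If sites instead logged withheld capsules as not taken, SAP compliance = c(S − w)/S. For w = 24 this is 0.90 × 360/384 = 84.4%, an understatement. The SAP does not say which applies.

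**3. Exposure, Combined Data, if the span is continuous.** Full dosing is 96 + 384 = 480 weeks.
- Entry gap of 26 weeks (about 6 months): 506/480 = +5.4%
- Parent-study time off BG00012 on other therapy: 24 weeks, 480/456 = +5.3%; 48 weeks, 480/432 = +11.1%; 84 weeks, 480/396 = +21.2%
- 26-week gap plus 48 weeks on other therapy: 506/432 = +17.1%

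Neither source enters the 109MS303-only exposure or the compliance figure.

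**4. Cohort effect.** For a share f of subjects with a resumed withholding, overstatement = fw/(S − fw). The Protocol's amendment history puts lymphocyte counts below 0.5 × 10⁹/L for at least six months at 2% of subjects; f = 0.02 borrows that as a scale.
- S = 384: w = 8 gives 0.16/383.84 = 0.04%; w = 96 gives 1.92/382.08 = 0.50%
- S = 260 (an assumed shorter mean): w = 8 gives 0.06%; w = 96 gives 1.92/258.08 = 0.74%
- Stress case, f = 0.05, w = 96, S = 260: 4.8/255.2 = 1.9%

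For the gap, a share g with 26 weeks adds g × 26/480: 0.3%, 1.1% and 2.7% at g = 5%, 20% and 50%. The documents give neither this share nor that of switchers.

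**The case against.** The strongest reply is that little of consequence depends on these summaries. Adverse event incidence is a proportion of subjects (SAP 6.5.3), the ARR uses follow-up time (SAP 6.4.3), primary safety analyses use 109MS303 data only (SAP 6.5.1), and the analyses are generally descriptive (SAP 6.1). Assessments continue while drug is withheld (Protocol 11.2.1). The SAP also reports time on study before alternative MS medication (6.3.6) and the number of subjects who used such medication in the parent studies (6.3.7). All of this stands and limits the damage. It does not correct the exposure figure: time on study is not time on drug.

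Three stronger inferences are tempting, and the documents do not support them.

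- **That all three sources inflate compliance.** Compliance is confined to 109MS303, so the entry gap and parent-study therapy cannot change it.
- **That the gap and switcher time are certainly counted.** SAP 6.2.3 treats Combined Data as one dataset, and SAP 6.3.8 counts visit days from the first dose in a dataset, which makes a continuous span the natural reading. SAP 6.3.6 does not say so. Summing by study would remove the gap and could remove the switcher time.
- **That the worst lymphopenia cases are the most distorted, or that compliance looks best where withholding was longest.** Under Protocol Table 3, counts still below 500/mm³ after 24 weeks off drug lead to permanent discontinuation, and subjects given alternative therapy may not restart. Such cases add no off-drug time to the span. The same holds for ALT/AST elevations that persist (Table 1).

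**Conclusion.** The concern holds in a limited form. As written, SAP 6.3.6 overstates exposure for every subject who restarts after a withholding, in both datasets. In Combined Data it also counts the entry gap and parent-study off-drug time if the span is continuous. Compliance is overstated for restarted subjects on the natural reading of capsules due, and understated if sites recorded withheld capsules as missed; either way the definition is incomplete.

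The effect can be material for an individual: +6.7% for 24 weeks in 384, +5.4% for a 26-week gap, and about +5% to +21% for 24 to 84 parent-study weeks on other therapy. For the cohort, withholding alone is probably below 1%, which rests on the assumed 2% share. Adverse event incidence tables do not change. This is a correction to reported exposure and compliance, not a threat to the safety conclusions.

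**What to change.** In SAP 6.3.6:

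1. Define BG00012 exposure as the sum of dosed intervals, net of recorded interruptions, and derive subject-years and duration categories from it.
2. For Combined Data, state that BG00012 dosed time is summed by study. Exclude the interval from the last parent-study BG00012 dose to the first 109MS303 dose. Also exclude parent-study placebo or GA time. The SAP's term is study medication, so for those starters a continuous span would be 480 weeks against 384 on BG00012 (+25%) if presented as BG00012 exposure.
3. Derive capsules assigned from the days and capsules per day actually prescribed: 6 in the dose-blind phase and 4 open-label (Protocol 10.1), with the prescribed number during a dose reduction. State how withheld capsules on the accountability page are treated, so that numerator and denominator match.
4. Keep the first-to-last span only under the label treatment duration.

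The cost is a small amount of programming, with slightly lower subject-years and, on the natural reading, slightly lower compliance. SAP 6.5.6 already uses interruption start dates. The availability of restart dates and parent-study off-drug dates should be confirmed, because the documents do not show them.
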